7 MEASUREMENTS OF TREATMENT COMPLIANCE

During Part A1 of this study, administration of study treatment will be performed via iv infusion at the study site under the supervision of the designated site personnel and in compliance with the Guideline for First in Human clinical studies (EMEA/CHMP/SWP/28367/07Rev. 1). Compliance will be monitored at the site through a review of accountability logs which will be used to record study treatment dispensing and return information to ensure that each study participant received the correct dose level and frequencies of dosing (e.g. Q3W, Q4W).

Any dosing deviations will be reviewed as IPDs at the DEMs and assessed for possible impact on the PPS and PKS. If considered important, these deviations will be included in the summary and listing of IPDs.

8 SAFETY ANALYSES

All safety summaries and listings will be presented by treatment group based on the SS, unless otherwise stated.

All safety summaries will be programmed by tumor type (CRC, Gastric/GEJ-Cancer and Pancreatic Adenocarcinoma) depending on the number of participants with specific tumor types and may be presented in the CSR.

8.1 Extent of exposure

Details on UCB6114 administration on Day 1 (all cohorts) and Day 15 (Cohort 1 and 2 only) of each cycle will be listed. This listing will be split into two parts. The first part will include the start and stop dates and times of infusion, duration of infusion, infusion rate, whether the infusion was temporarily stopped/interrupted, whether the infusion was permanently discontinued and, if this was the case, whether the interruption or permanent discontinuation was due to an AE or other reason. The second part of this listing will include, for each visit, infusion site, total volume delivered, volume infused, planned total dose and total dose actually administered at infusion. In addition, the percentage of planned dose received, total dose administered across all cycles, the number of complete cycles of UCB6114 received and the total number of doses of UCB6114 received will be listed.

The percentage of planned dose received will be calculated for UCB6114 for each study participant at each dosing visit within each cycle as follows:

$$\text{Percentage of Planned Dose Received} = 100 \times \frac{\text{Total Dose Administered}}{\text{Planned Total Dose}}$$

Actual duration of infusion will be calculated in minutes only for those study participants who did not have any temporary interruption(s) of their infusion using the infusion start and stop times and included on this listing. Length of interruption(s) will be calculated in minutes for those study participants who had temporary interruption(s) of their infusion.

Extent or duration of exposure will be calculated and summarized. Frequency counts and percentages for the number of complete cycles of UCB6114 received (0, 1, 2, 3, 4, >4) and summary statistics for the total dose of UCB6114 received across all cycles, the total number of doses of UCB6114 received and the duration of exposure to UCB6114 will be presented.

Total duration of exposure will be calculated in days as follows:

$$\text{Total Duration of Exposure} = (\text{Date of Last Dose} - \text{Date of First Dose}) + 30$$

Note that 30 days is added to this calculation to account for a participant's continued exposure to UCB6114 following their last dose of study treatment.

Note that the definition of a participant deemed to have completed a full cycle of UCB6114 is given in [Section 5.1](#).

8.2 Adverse events

The primary safety endpoints for Part A1 of this study are the incidence and severity of TEAEs (including SAEs) from the first dose of UCB6114 treatment on Day 1 of Cycle 1 until the end of the SFU Period (up to 30 days following the last dose of UCB6114), and the incidence of DLTs from the first dose of UCB6114 on Day 1 of Cycle 1 until the end of the DLT Observation Period (Day 28 of Cycle 1).

All AEs for a participant will be recorded in the eCRF from the time of informed consent until completion or early discontinuation of Part A1 of this study. Serious adverse events are to be reported up to 30 days after the Final Visit (i.e. up to 150 days after the last dose of UCB6114). All AEs in Part A1 of the study will be coded using MedDRA® and classified as pre-treatment and treatment-emergent relative to the first infusion of UCB6114.

Adverse events with a start date prior to the first dose of UCB6114 will be defined as pre-treatment AEs. A TEAE is defined as any AE with a start date on or after the first dose of UCB6114 up until the last dose of UCB6114 + 30 days. A pre-treatment AE which increases in severity on or after the first dose of UCB6114 will also be counted as a TEAE. Note that in this case, the pre-existing AE will have a stop date and an outcome of 'worsened' and a new AE (with the same verbatim) will be entered with the same start date and the increased severity recorded on the eCRF. Any AE (including SAEs) with an onset date later than the last dose of UCB6114 + 30 days will not be considered as treatment-emergent and therefore will not be included in the tabulations of TEAEs. These AEs will be considered as post-study AEs and will be listed only. Where onset dates are missing or partially missing, AEs will be assumed to be treatment-emergent, unless there is clear evidence to suggest that the AE started prior to the first dose of UCB6114 and did not increase in severity. Missing or partially missing dates for AEs will be handled as described in [Section 4.4.1](#).

Adverse events will be assigned an NCI CTCAE severity grade (Grade 1/Grade 2/Grade 3/Grade 4/Grade 5), where possible. If a CTCAE toxicity grading is not possible, then the intensity of the AE (mild/moderate/severe) will be recorded on the eCRF. If the AE is not gradable, is serious, and is considered as life threatening, then the intensity for this AE will be missing and one of the reasons for seriousness will be recorded as life threatening.

Adverse events will also be categorized according to their relationship to UCB6114 (related/not related), and whether the event is a DLT, as judged by the investigator. A DLT is defined as a TEAE at least possibly related to UCB6114 that occurs during Cycle 1 and fulfills any of the criteria listed in Section 4.1.2.4 of the protocol. The investigator is expected to record whether an AE is a DLT on the eCRF.

An overview of the number and percentage of participants who experience TEAEs will be presented. This summary will include the number and percentage of participants with any TEAEs, serious TEAEs, related TEAEs (related to UCB6114), discontinuations from study treatment (UCB6114) due to TEAE(s), discontinuations from the study due to TEAE(s), CTCAE Grade ≥ 3 TEAEs, CTCAE Grade ≥ 3 related TEAEs, DLTs, AEs leading to death and TEAEs leading to death; event counts will also be included against each of these categories. The overview of TEAEs may be presented by tumor type (CRC, Gastric/GEJ-Cancer and Pancreatic Adenocarcinoma) depending on the number of participants with specific tumor types.

In addition, the following summaries will be presented by SOC, high level term (HLT) and PT, and, where indicated, also by tumor type (CRC, Gastric/GEJ-Cancer and Pancreatic Adenocarcinoma) depending on the number of participants with specific tumor types:

- Incidence of TEAEs (overall and by tumor type);
- Incidence of serious TEAEs (overall and by tumor type);
- Incidence of non-serious TEAEs (overall and by tumor type);
- Incidence of TEAEs leading to a temporary interruption of study treatment infusion and/or dose reduction (overall and by tumor type);
- Incidence of TEAEs leading to discontinuation of study treatment (overall and by tumor type);
- Incidence of TEAEs leading to discontinuation of study (overall and by tumor type);
- Incidence of DLTs (overall and by tumor type);
- Incidence of adverse events of special interest (AESIs) (Potential Hy's Law – see [Section 8.2.1](#) below) (overall and by tumor type);
- Incidence of UCB6114 infusion-related reactions (defined as hypersensitivity reactions, anaphylactic reactions and cytokine release syndrome – see [Section 8.2.2](#)) (overall and by tumor type);
- Incidence of TEAEs by maximum CTCAE severity grade (overall and by tumor type);
- Incidence of TEAEs by maximum relationship to UCB6114 (overall and by tumor type);
- Incidence of TEAEs by relationship;
- Incidence of serious TEAEs by relationship;
- Incidence of non-serious TEAEs by relationship;
- Incidence of fatal TEAEs by relationship;
- Incidence and event rate of TEAEs by treatment-emergent ADA positivity.

The following summaries will be presented by SOC and PT for EudraCT reporting:

- Incidence of non-serious TEAEs above the threshold of 5% of participants in any treatment group;

- Incidence of non-serious TEAEs above the threshold of 5% of participants in any treatment group by relationship;

The above summaries of TEAEs will be ordered alphabetically by SOC, alphabetically by HLT within SOC and decreasing incidence of PT events within SOC /HLT in all study participants. For tables including only the number and percentage of participants, summaries will be ordered alphabetically by SOC, alphabetically by HLT within SOC and decreasing incidence of participants with each PT within SOC /HLT in all study participants.

The incidence of TEAEs by maximum CTCAE severity grade will be presented by CTCAE term. CTCAE term will be obtained from the NCI CTCAE Version 5.0 via a mapping of MedDRA® lowest level terms (LLTs). This summary will be ordered by decreasing incidence of participants with each CTCAE term in all study participants.

Summary tables will contain frequency counts and percentages, and the number of events, where applicable. A study participant who experiences the same event multiple times will be counted only once in the frequency counts for the PT, but all events will be included.

In the summaries of TEAEs by relationship, participants will be counted in “Not related” and “Related” categories (or “Missing” in the case where an event has a missing relationship). A study participant who experiences the same event multiple times will be included in the most related category for the summaries by maximum relationship.

In the overview summary of TEAEs, participants will be counted as having at least one TEAE with CTCAE severity grade ≥ 3 , and in the summary of TEAEs by maximum CTCAE severity grade, participants will be counted as having at least one TEAE in the following categories: ‘Grade 1’, ‘Grade 2’, ‘Grade 3’, ‘Grade 4’, ‘Grade 3 or 4’, ‘Grade 5’, and ‘Grade ≥ 3 ’. Events for which no CTCAE severity grade is recorded by the investigator but an intensity is recorded instead, the intensity of this event will be assigned to a CTCAE severity grade for the purpose of these summaries, i.e. ‘Mild’ will be included as ‘Grade 1’, ‘Moderate’ will be included as ‘Grade 2’, ‘Severe’ will be included as ‘Grade 3’ and ‘Life Threatening’ will be included as ‘Grade 4’ and, if the participant dies due to the event, it will be included as ‘Grade 5’. The determination of whether the event is life threatening or results in death will be based on the reason for seriousness recorded as life-threatening or death on the eCRF, or on the event having a fatal outcome. Otherwise, if both the CTCAE severity grade and intensity is missing then the CTCAE severity grade in these summaries will be missing. A study participant who experiences the same event multiple times will be included in the highest severity grade category in the summary of TEAEs by maximum CTCAE severity grade.

A glossary of all AEs will be presented including the MedDRA® SOC, HLT, PT, reported term and LLT.

A listing of all AEs will be presented by study participant for the ES. The listing will include the onset date and stop date of the event (including relative days) and also the onset times and stop times of events where available. The period of onset of AEs will also be presented on this listing.

Period of onset of AEs will be defined as follows for the purpose of the listing:

- If the AE has an onset date prior to the date of the Screening visit, then Period=Pre-study;

- If the AE has an onset date on or after the date of the Screening visit and has an onset date and time prior to the start time of UCB6114 infusion on Day 1 of Cycle 1 then Period=Screening;
- If the AE has an onset date and time on or after the start time of UCB6114 infusion on Day 1 of Cycle 1 and up to the date and time of the start of Cycle 2 (i.e. prior to the start time of the UCB6114 infusion on Day 1 of Cycle 2) then Period=Cycle 1;
- If the AE has an onset date and time on or after the start time of UCB6114 infusion on Day 1 of Cycle 2 and up to the date and time of the start of Cycle 3 (i.e. prior to the start time of the UCB6114 infusion on Day 1 of Cycle 3) then Period=Cycle 2;
- Same as above for subsequent cycles (Cycle 3 etc.);
- If the AE has an onset date after the last dose of UCB6114 up to and including 30 days after the last dose of UCB6114, then Period=SFU;
- If the event has an onset date after the 30-day period following the last dose of UCB6114, then Period=Post-study.

The listing of all AEs will also include the AE duration (derived in days, hh:mm for AEs with onset and stop times recorded and derived in days for all other AEs with only onset and stop dates recorded), days since start of UCB6114 infusion (time if an onset time is recorded, days otherwise), seriousness and reason for seriousness, CTCAE severity grade, intensity (where a CTCAE severity grade is not recorded), pattern of event, relationship to UCB6114 and action taken with UCB6114 (including other action taken), the outcome of the AE, whether an autopsy was performed and cause of death. In addition, the listing will flag AEs that led to discontinuation from the study, TEAEs, AESIs, SAEs, infusion-related reactions, and DLTs. Whether an AE is related to a concomitant medication (which will include the COVID-19 vaccination) and the names of any co-suspect medications will also be listed.

Separate listings of all SAEs, TEAEs leading to discontinuation of UCB6114 and TEAEs leading to discontinuation of the study will also be presented.

All deaths that occur on study (defined as during study treatment or within 30 days of the latest dose of UCB6114) will be listed separately. This listing will include the primary cause of death and the number of days between the date of the last dose of UCB6114 and death, defined as

$$\text{Days since last dose} = (\text{Date of death} - \text{Date of last dose of UCB6114}) + 1$$

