2.2 Study endpoints

2.2.1 Safety endpoints

2.2.1.1 Primary safety endpoints

The primary endpoints for Part A1 of this study are for safety, specifically the incidence and severity of treatment-emergent adverse events (TEAEs) (including serious adverse events [SAEs]) from the first dose of UCB6114 on Day 1 of Cycle 1 to the Safety Follow-up (SFU) visit, and the incidence of dose limiting toxicities (DLTs) from the first dose of UCB6114 on Day 1 of Cycle 1 to the end of the 28-day DLT Observation Period for all cohorts.

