2.3 Study design and conduct

Study ONC001 is a multicenter, nonrandomized, open-label, Phase 1/2 study evaluating the safety, PK, efficacy (as assessed by antitumor activity), PD, biomarkers, and immunogenicity (ADA activity) of intravenous (iv) UCB6114 as monotherapy and in combination with selected standard of care (SOC) regimens in study participants with advanced solid tumors.

The study has a modular design including up to 3 dose escalation modules (Parts A, B, and C), 1 dose optimization module (Part A1), and up to 4 dose expansion modules (Parts D, E, F, and G). Depending on emerging data, not all modules may open. This SAP is focused only on the dose optimization module of the study to evaluate alternative dosing schedules for UCB6114 administered as monotherapy in participants with unresectable locally advanced or metastatic colorectal adenocarcinoma, gastric adenocarcinoma, adenocarcinoma of the gastroesophageal junction, or pancreatic adenocarcinoma.

Part A1 consists of a Screening Period, Treatment Period (consisting of 28-day cycles for Cohorts 1, 2, and 4, and of 21-day cycles for Cohort 3), a SFU visit and a Final Visit. During the Treatment Period, UCB6114 will be administered as iv infusion as per the defined dosing

schedules in Table 6-6 of the protocol until the occurrence of progressive disease, unacceptable toxicity, or withdrawal of consent.

Part A1 will be initiated after Cohort 5 of Part A (2000mg every 2 weeks [Q2W]) has been determined to be safe (i.e. DLT incidence <33%, see Section 4.1.2.4 of the protocol). Eligible participants with unresectable locally advanced or metastatic colorectal adenocarcinoma, gastric adenocarcinoma, adenocarcinoma of the gastroesophageal junction, or pancreatic adenocarcinoma will receive iv infusion of UCB6114 as monotherapy.

[figure not shown]
The planned dose optimization scheme for Part A1 will assess the safety and tolerability of the new drug formulation and will explore shortening of the infusion time and less frequent dosing as follows:

- Cohort 1: 2000mg Q2W (60-minute iv infusion), 28-day treatment cycle
- Cohort 2: 2000mg Q2W (30-minute iv infusion), 28-day treatment cycle
- Cohort 3: 3000mg every 3 weeks (Q3W) (90-minute iv infusion), 21-day treatment cycle
- Cohort 4: 4000mg every 4 weeks (Q4W) (120-minute iv infusion), 28-day treatment cycle

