3.2.2 Study periods

Part A1 of the study will consist of the following study periods:

- Screening Period – up to 28 days;
- Treatment Period – Successive 28-day cycles for Cohorts 1, 2, and 4, and 21-day cycles for Cohort 3. UCB6114 is administered as iv infusion as per defined dosing schedules until the occurrence of progressive disease, unacceptable toxicity, or withdrawal of consent;
- Safety Follow-up Period – up to 30 days after the last dose of UCB6114.

There will be a further extended follow-up period, up to 3 months after the last dose of UCB6114, at which time the Final Visit will be performed.

For each participant, the end of the Treatment Period is defined by the date of their last dose of UCB6114.

The end of Part A1 of the study is defined by the date of the Final Visit for the last participant (3 months after the last participant’s last dose of UCB6114), or the date of the SFU visit, if they discontinue prior to attending the Final Visit, or their last contact date if they discontinue early from the study without attending the SFU visit.

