3.5.7 DLT Evaluable Set (DES)

The DLT Evaluable Set (DES) will include all study participants who, during the 28-day DLT Observation Period, receive the planned dose of UCB6114.

The DES will be used only for evaluations by the SMC to determine if a dosing schedule and Part A1 can continue as planned.

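### Part A1 gives the primary DLT endpoint two windows in Cohort 3 (28 days, or a 21-day Cycle 1), so related events on Days 22 to 28 may not be counted as DLTs

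*SAP*

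**What the plan says.** All references are to the Part A1 SAP unless stated otherwise.

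- Section 2.2.1.1 defines the primary DLT endpoint as incidence from the first dose "to the end of the 28-day DLT Observation Period for all cohorts".
- Section 3.5.7 builds the DLT Evaluable Set on the same period, requiring that participants, "during the 28-day DLT Observation Period, receive the planned dose of UCB6114". Sections 2.3 and 4.7 also time the SMC reviews by 28 days.
- Section 8.2 restates the primary endpoint as running "until the end of the DLT Observation Period (Day 28 of Cycle 1").
- Section 8.2 then defines the event: "A DLT is defined as a TEAE at least possibly related to UCB6114 that occurs during Cycle 1", subject also to the criteria in protocol Section 4.1.2.4.
- Cycle length differs by cohort. Section 3.2.2 has "Successive 28-day cycles for Cohorts 1, 2, and 4, and 21-day cycles for Cohort 3", and Section 2.3 has "Cohort 3: 3000mg every 3 weeks (Q3W) (90-minute iv infusion), 21-day treatment cycle".
- For the AE listing, Section 8.2 closes the first cycle just before the next cycle's infusion: "prior to the start time of the UCB6114 infusion on Day 1 of Cycle 2) then Period=Cycle 1".
- On who decides, Section 8.2 says: "The investigator is expected to record whether an AE is a DLT on the eCRF".

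**The concern.** In Cohorts 1, 2 and 4 a cycle lasts 28 days, so a limit of Cycle 1 and a limit of 28 days mean the same thing. In Cohort 3 they do not. An event on Days 22 to 28 falls inside the observation period of the primary endpoint and outside the DLT definition in Section 8.2. The days in question begin with the scheduled second infusion.

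The likely cause is text carried over from Part A. Section 8.2 of the Part A SAP has nearly the same two statements, and they are consistent there because every Part A cycle is 28 days. Section 2.2.1.1 was adapted for Part A1 and Section 8.2 was not.

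At stake is a primary endpoint in a cohort of up to 8 participants. A DLT also has a consequence beyond the table: under Sections 2.3 and 4.7, 1 or more DLTs in a cohort leads to an ad hoc SMC meeting. An event that is not labelled a DLT does not set that off.

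**Working it through.** **1. The two windows, cohort by cohort (on schedule)**

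| Cohort | Cycle length | Infusions in Days 1–28 | End of window, Section 2.2.1.1 | End of window, Cycle 1 wording in Section 8.2 |
|---|---|---|---|---|
| 1 and 2 | 28 days | Days 1 and 15 | Day 28 | Day 28 |
| 3 | 21 days | Days 1 and 22 | Day 28 | Day 21 |
| 4 | 28 days | Day 1 | Day 28 | Day 28 |

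Only Cohort 3 differs. The gap is 28 − 21 = 7 days (Days 22 to 28), and 7/28 = 25% of the window. If Cycle 2 is delayed, Cycle 1 lengthens and the gap narrows for that participant.

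**2. Illustrative effect on the observed rate**

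The SAP does not say how DLT risk is spread over the 28 days. Assume a constant hazard, so that the 21-day risk is 1 − (1 − p)^(21/28), where p is the 28-day risk.

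- p = 33%, the maximum tolerable rate in Section 2.4: 1 − 0.67^0.75 = 0.259, a shortfall of about 7 percentage points.
- p = 10%, an assumed lower rate: 1 − 0.90^0.75 = 0.076, a shortfall of about 2.4 points.

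In a cohort of 8, a single unflagged DLT changes the incidence by 1/8 = 12.5 points.

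**3. Illustrative effect on the stated operating characteristic**

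Section 2.4 gives a probability of 80% of declaring a schedule too toxic when Part A1 is taken alone. It states no cut-off, so one was searched for. With X binomial (n = 8, p = 0.33):

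- P(X ≥ 1) = 0.959
- P(X ≥ 2) = 0.799
- P(X ≥ 3) = 0.524

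A cut-off of 2 of 8 reproduces the 80%. Keeping that inferred cut-off, P(X ≥ 2) in Cohort 3 with only 21 days counted is:

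| Assumption on timing | 21-day rate | P(X ≥ 2) |
|---|---|---|
| 10% of DLTs start on Days 22–28 | 0.33 × 0.90 = 0.297 | 0.739 |
| 25% | 0.33 × 0.75 = 0.2475 | 0.627 |
| 40% | 0.33 × 0.60 = 0.198 | 0.491 |
| Constant hazard | 0.259 | 0.656 |

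The cut-off and the timing are both assumptions. What does not depend on them is the direction: a shorter window cannot raise the count.

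**The case against.** The strongest reply is that nothing in the SAP removes these events by program. DLT status is the investigator's judgement, entered on the eCRF, and the cycle boundary in Section 8.2 serves the AE listing only. A site working to 28 days would flag a Day 25 event and it would be tabulated. The weight of the text also favours 28 days: Sections 2.2.1.1, 2.3, 3.5.7 and 4.7 all use it, and the endpoint statement in Section 8.2 reads most naturally as Day 28 with the wrong cycle label. One phrase stands against them. This reply stands, and it limits the finding to a risk. It does not remove the conflict, because that phrase is the definition of the event, no sentence gives priority to the other wording, and no check of the flag against the 28-day period is described.

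A reader might go further and infer that DLTs on Days 22 to 28 are lost, or that Cohort 3 is followed for 7 fewer days. The SAP supports neither. Whether an event is missed depends on how the investigator applies the definition, and on protocol Section 4.1.2.4 and the eCRF guidance, which are not at hand. Follow-up is not shortened: AEs are recorded until completion or early discontinuation of Part A1, and TEAEs run to 30 days after the last dose. A Day 22 to 28 event would still appear in the TEAE tables and, as applicable, in the serious, related and Grade 3 or higher summaries, and in the safety data the SMC reviews.

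A reader might also infer that one common window would make the cohorts comparable infusion for infusion. It would not. Cohort 4 has one scheduled infusion in 28 days by design, and the SAP plans no formal comparison between cohorts.

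**Conclusion.** The contradiction is certain and concerns a primary endpoint in one cohort only. Its consequence is conditional. If the Cycle 1 wording is followed, Cohort 3's DLT incidence could be biased low and the ad hoc SMC trigger could be missed, while the events remain visible as TEAEs.

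The firm figure is the affected span: 7 of 28 days, or 25% of the window, starting with the scheduled second infusion. The effect on the rate is unknown. The readings of about 26% for a true 33%, and about 7.6% for a true 10%, rest on a constant hazard; 33% is the maximum tolerable rate and not an expected one. The fall from 0.80 to about 0.66 also rests on a cut-off that the SAP does not state. None of these should be quoted as the size of an actual bias.

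The point should still be corrected before lock, because as written the plan allows two different DLT counts for the same Cohort 3 data.

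**What to change.** - In Section 8.2, replace the Cycle 1 limit in the DLT definition with the DLT Observation Period of Section 2.2.1.1, counted in study days from first dose, so that the definition and the period use one window in every cohort.
- In the endpoint statement of Section 8.2, remove the parenthetical label that places Day 28 in Cycle 1.
- Check that protocol Section 4.1.2.4, the eCRF guidance for the DLT question and the derivation of the DES use that same window for Cohort 3. If any of them uses another window, the texts must be reconciled.
- If Cohort 3 participants have already been treated, review their related AEs with onset on Days 22 to 28 and query the DLT flag where the answer may have turned on the cycle wording.

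The cost is two sentences in the SAP and a document check. No new data are needed, because AE onset dates are already collected.

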Up to 32 participants will be allocated 1:1:1:1 to one of the 4 cohorts, with each cohort enrolling up to 8 study participants including 1 sentinel participant with an observation period of 48 hours. The enrollment of a sentinel participant in each cohort has been included as an additional risk mitigation measure to monitor infusion related reactions and other early onset treatment-related AEs.

The planned duration of study treatment is 2 cycles. Participants may, however, remain in the study for additional cycles if they are receiving therapeutic benefit (stable disease [SD], partial response [PR], or complete response [CR]) or until they fulfill one of the criteria for study treatment discontinuation. Participants will continue study treatment until disease progression, unmanageable toxicity, or withdrawal of consent. Upon discontinuation from study treatment, participants will be referred to appropriate follow-up care per the investigator's judgment.

A schematic diagram of Part A1 of the study is provided in [Figure 2-1](#).

Figure 2-1: Study Schematic for Part A1

* Cohorts 1, 2, and 4: 28-day treatment cycles; Cohort 3: 21-day treatment cycles

D=day; iv=intravenous; Q2W=every 2 weeks; Q3W=every 3 weeks; Q4W=every 4 weeks

A Safety Monitoring Committee (SMC) will convene after each sentinel participant is assessed for at least 48 hours following the first administration of UCB6114 in the first cycle of a cohort to determine whether further participants within the cohort can be enrolled. The SMC will also convene after 25%, 50% and 100% of study participants in Part A1 have completed the required 28-day DLT Observation Period. If deemed necessary, an additional SMC meeting can convene after 75% of the participants have completed the required 28-day DLT Observation Period. If 1 or more DLTs are reported for a cohort then an *ad hoc* SMC will convene to determine if the dosing schedule and study module can continue as planned.

After consultation, the SMC will provide recommendations which could include an expansion of enrollment in a particular cohort to gain additional safety data, continuation of Part A1 with modifications or a temporary suspension of enrollment in a particular cohort. Details are described in the Part A1 SMC Charter.

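### Crude TEAE and infusion-reaction percentages are not directly comparable across the Part A1 schedules; add per-infusion and common-window summaries by cohort

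*SAP*

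**What the plan says.** All references are to the Part A1 SAP.

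- **Schedules (Section 2.3).** "Cohort 1: 2000mg Q2W (60-minute iv infusion), 28-day treatment cycle"; the second cohort has the same interval and cycle length with a shorter infusion of half an hour. The next step lengthens the interval: "Cohort 3: 3000mg every 3 weeks (Q3W) (90-minute iv infusion), 21-day treatment cycle". The longest interval comes last in the list: "Cohort 4: 4000mg every 4 weeks (Q4W) (120-minute iv infusion), 28-day treatment cycle".
- **Duration (Section 2.3).** "The planned duration of study treatment is 2 cycles", but treatment is open-ended: "Participants will continue study treatment until disease progression, unmanageable toxicity, or withdrawal of consent".
- **TEAE window (Section 8.2).** Counting starts at the first dose and runs "up until the last dose of UCB6114 + 30 days".
- **IRR definition (Section 8.2.2).** Onset must fall within 24 hours of the start of an infusion.
- **Reporting (Sections 3.1, 8 and 8.2).** Summaries are by dose schedule cohort. For TEAEs and IRRs: "Summary tables will contain frequency counts and percentages, and the number of events, where applicable". The only rate named is "Incidence and event rate of TEAEs by treatment-emergent ADA positivity".
- **Exposure (Section 8.1).** Number of doses, total dose and duration of exposure are summarised by cohort, in separate tables.
- **DLTs (Section 2.2.1.1).** A 28-day observation period applies to all cohorts.

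**The concern.** TEAE incidence is part of the primary endpoint. IRRs are one of the early harms that the sentinel step in Section 2.3 is meant to catch. Both are tabulated in adjacent columns for schedules that give different numbers of infusions and, because the TEAE window hangs on the last dose, different lengths of observation. Each infusion opens a new 24-hour IRR window, so a cohort with twice the infusions has twice the opportunities. Raw event counts have the same limitation.

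Two misreadings are possible. A lower percentage in Cohort 3 or 4 may reflect only fewer infusions or a shorter window. Conversely, similar percentages may hide a higher risk per infusion at the larger amounts. No by-cohort TEAE or IRR table in Section 8.2 has a person-time or per-infusion denominator that would separate these readings.

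**Working it through.** The SAP gives no expected TEAE or IRR rate, so there is no planned figure to reproduce on this point. The 80% in Section 2.4 concerns declaring a schedule too toxic. It matches two or more events among 8 at 33%: 1 − 0.67^8 − 8 × 0.33 × 0.67^7 = 0.799. That cut-off is inferred, and the figure does not bear on the issue here.

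**Step 1: opportunity over the planned 2 cycles.** Dose days follow from the Section 2.3 schedules; the last TEAE day is the last dose day + 30.

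| | Cohorts 1 and 2 | Cohort 3 | Cohort 4 |
|---|---|---|---|
| Dose days | 1, 15, 29, 43 | 1, 22 | 1, 29 |
| Infusions | 4 | 2 | 2 |
| Last TEAE day | 43 + 30 = 73 | 22 + 30 = 52 | 29 + 30 = 59 |

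**Step 2: IRRs with the same risk q at every infusion (assumed).** Participant percentage = 1 − (1 − q)^k for k infusions.

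| q | k = 4 (Cohorts 1, 2) | k = 2 (Cohorts 3, 4) |
|---|---|---|
| 2% | 7.8% | 4.0% |
| 5% | 18.5% | 9.8% |
| 10% | 34.4% | 19.0% |
| 20% | 59.0% | 36.0% |

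**Step 3: TEAEs with the same constant hazard (assumed).** With risk m per 28 days, h = −ln(1 − m)/28, and the percentage over w days is 1 − exp(−h × w).

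| m | w = 73 | w = 52 | w = 59 |
|---|---|---|---|
| 5% | 12.5% | 9.1% | 10.2% |
| 20% | 44.1% | 33.9% | 37.5% |
| 30% | 60.5% | 48.4% | 52.8% |
| 50% | 83.6% | 72.4% | 76.8% |

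**Step 4: size with 8 per cohort.** At m = 20% the expected counts are 3.5, 2.7 and 3.0. Over the m values shown, the largest TEAE gap is 8 × (60.5% − 48.4%) = 1.0 participant. For IRRs the gap is 0.7 at q = 5%, 8 × (34.4% − 19.0%) = 1.2 at 10%, and 8 × (59.0% − 36.0%) = 1.8 at 20%. At m = 20%, Cohort 1 shows more affected participants than Cohort 4 with probability only 0.51, and they tie with probability 0.19.

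**Step 5: treatment beyond 2 cycles.** Suppose all cohorts are dosed for the same calendar time.

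| Dosing through | Infusions, Cohorts 1–2 / 3 / 4 | Last TEAE day |
|---|---|---|
| Day 56 | 4 / 3 / 2 | 73 / 73 / 59 |
| Day 112 | 8 / 6 / 4 | 129 / 136 / 115 |

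The infusion imbalance persists. The window difference for Cohort 3 disappears at Day 56 and is reversed at Day 112.

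**Step 6: unequal risk per infusion.** Suppose risk rises with the amount infused, so that the 2-cycle percentage is 1 − (1 − q)^(total mg/2000). Totals are 8000, 6000 and 8000 mg for Cohorts 1–2, 3 and 4. At q = 5% the crude percentages are 18.5%, 14.3% and 18.5%. Cohorts 1–2 and 4 look identical, yet the risk per infusion is 5% in one and 1 − 0.95² = 9.8% in the other.

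**The case against.** A reader might infer that the less frequent schedules look safer by construction. The documents do not support that as a general statement. The Day 52 and Day 59 limits apply only if everyone stops after 2 cycles, whereas treatment continues to progression, toxicity or withdrawal. The first tumor assessment is targeted at Day 57 (Section 10.1.2), after two 21-day cycles have ended. Equal risk per infusion is also only an assumption: the infusions differ in amount and duration, and reactions concentrated at the first infusion would leave the crude percentages nearly comparable.

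Further points stand in the plan's favour. It is descriptive, and no formal comparison of schedules is planned. Participant-level incidence is a legitimate summary, and fewer reactions from fewer infusions can be a real property of a schedule. Section 8.1 gives doses and exposure by cohort, and the adverse event listing carries time since infusion and an IRR flag, so individual reactions can be traced. The DLT component has a stated common window.

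These points limit the size and certainty of the concern. They do not supply the missing denominator, and Step 6 shows that risk rising with dose is a situation in which the crude table would mislead.

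A person-time rate has its own weakness. If events cluster early and affect equal numbers in each cohort, dividing by 52 or 59 days instead of 73 makes Cohorts 3 and 4 look 73/52 = 1.40 and 73/59 = 1.24 times as bad.

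**Conclusion.** The point holds as a matter of comparability. At the planned 2 cycles and equal underlying risk, the crude percentages favour Cohorts 3 and 4. The expected distortion is about one participant or less for TEAEs and for an IRR risk of 5% per infusion; it passes one only at assumed IRR risks of about 10% or more. At 8 per cohort this is within chance variation. All hazards and per-infusion risks are assumptions, shown as ranges. The direction is not fixed for TEAE windows once treatment continues. The IRR part is the firmer one, because at equal calendar time the Q2W cohorts always receive more infusions. This is an inexpensive improvement to descriptive tables and does not invalidate the planned summaries.

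**What to change.** In Section 8.2, add the following by cohort, descriptively, alongside the crude percentages:

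1. **IRRs:** events per infusion administered, and the percentage of participants with an IRR at the first infusion.
2. **Any, related and Grade ≥3 TEAEs:** incidence within a common window from first dose, for example the first 28 days, and/or an exposure-adjusted rate. Even a single dose keeps the TEAE window open to Day 31 (1 + 30), so 28 days fits every cohort. It equalises time but not infusions (2, 2, 2 and 1 in Cohorts 1 to 4), which is why item 1 is still needed.
3. **If a rate is given:** define time at risk to match the TEAE window (last dose − first dose + 31 days, truncated at death or last contact) and distinguish it from the Section 8.1 exposure duration, which adds 30. Footnote that the rate assumes a roughly constant hazard and can overstate risk in cohorts with shorter windows if events cluster early.

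The cost is SAP wording and a few table columns. Dose counts, dates and onset times are already collected. The rates will be imprecise at this sample size.

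Separately, Section 2.2.1.1 gives a 28-day DLT period for all cohorts, while the DLT definition in Section 8.2 refers to Cycle 1, which is 21 days in Cohort 3. These passages must be reconciled.
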